### 6.1.15. Subgroup Analyses

Some of the baseline severity of illness will be summarized and analyzed by comorbid diagnosis subgroup, which includes: CDI by MDD and non-MDD, CGI-Severity: Mental Illness by MDD/GAD and non-MDD/GAD, and MASC by GAD and non-GAD.

Suicide-related ideation and behavior, treatment-emergent suicidal ideation and behavior will also be analyzed by the following subgroups: patients with or without comorbid MDD;  $\geq$  or  $<$  the baseline median CDI score for the study. The Fisher's exact test will be used to overall compare the proportion of suicide-related events between the treatment groups. A logistic

regression model with factors of treatment, subgroup and treatment-by-subgroup will be performed to compare the proportion accounting for the subgroup effect.

For the BPI average pain severity, a subgroup analysis will be conducted for Study Period II. Table HMGW.6.14 lists the subgroup analysis variables by which the analyses performed.

To analyze a specific subgroup's impact, change from baseline to endpoint (LOCF and BOCF) in BPI average pain will be analyzed using an ANCOVA model with all the terms described generally in Section 6.1.2 and 6.1.3 with additional terms of the subgroup and the subgroup-by-treatment interaction. The primary statistical test will be for the treatment-by-subgroup interaction, which will be tested at the significance level of 0.05.

Furthermore, treatment group differences will be evaluated within each category of a subgroup regardless of the significance level of the treatment-by-subgroup interaction. For the subgroup of Race Origin, all the categories that have <10% of the patients in the study will be combined in the analysis. For the subgroup of NSAIDs use, the NSAIDs use is based on concomitant medication took during study and medical review.

Subgroup analysis for other efficacy and safety variables will be conducted as deemed appropriate and necessary.

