Treatment emergent/taper emergent suicidal ideation (category 1-5) compared to lifetime (or lead-in) baseline is defined as an increase in maximum suicidal ideation over lifetime (or lead-in) baseline during the study period, or any ideation during the study period, if there was none at lifetime (or lead-in) baseline. Treatment emergent/taper emergent suicidal behavior (category 6-10) compared to lifetime (or lead-in) baseline is defined as an increase in maximum suicidal behavior over lifetime (or lead-in) baseline during the study period, or any behavior during the study period, if there was none at lifetime (or lead-in) baseline. Emergence of serious suicidal ideation compared to lifetime (or lead-in) baseline is defined as an increase in the maximum suicidal ideation score to 4 or 5 during study period from no suicidal ideation (scores of 0) at lifetime (or lead-in) baseline. Improvement in suicidal ideation at endpoint compared to baseline is defined as a decrease in suicidal ideation score at endpoint (the last nonmissing measurement during study period) from the lead-in baseline. Treatment-emergent suicidal ideation or behavior compared to lifetime (lead-in) baseline is defined as an increase in maximum suicidal ideation or behavior over lifetime (or lead-in) baseline during the study period, or any ideation or behavior during the study period, if there was none at lifetime (or lead-in) baseline.

If the number of patients with post-baseline suicide-related events is greater than or equal to 4, then shift tables will be also be used to summarize the data. Table HMGW.6.11 and Table HMGW.6.12 are shells of format that show the number and percentage of patients with shifts between the most severe event category at baseline and the most severe event category post-baseline by treatment group, for Study Period II and lifetime baseline. Similar tables will be created for Study Period II and lead-in baseline, and Study Period III with both baselines if needed.

Subjects who discontinued from the study with no post-baseline C-SSRS value will be considered unevaluable for analyses of suicidality. Only evaluable subjects will be considered in the analyses.

Fisher's exact test will be used for treatment comparison for Study Period II. For each event, p-values will only be displayed if at least 4 events occurred in at least one treatment group.

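### The treatment-by-subgroup logistic model for suicide-related events makes no provision for an empty cell, and the floor of 4 events in one arm does not prevent one

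*SAP*

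**What the plan says.** SAP section 6.1.15 sets out a subgroup analysis of C-SSRS outcomes: "Suicide-related ideation and behavior, treatment-emergent suicidal ideation and behavior will also be analyzed by the following subgroups". The first split is "patients with or without comorbid MDD". The second is at or above versus below "the baseline median CDI score for the study". Two methods are named. One is an overall comparison: "The Fisher's exact test will be used to overall compare the proportion of suicide-related events between the treatment groups". The other is a logistic "regression model with factors of treatment, subgroup and treatment-by-subgroup will be performed to compare the proportion accounting for the subgroup effect". The model is planned without condition. No exact or penalized version, minimum cell count or fallback is given.

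Section 6.1.14.5 has two reporting floors for the same outcomes. For the Fisher comparison in Study Period II: "For each event, p-values will only be displayed if at least 4 events occurred in at least one treatment group". Shift tables are added on this condition: "If the number of patients with post-baseline suicide-related events is greater than or equal to 4". Section 6.1.15 does not say whether either floor applies to the logistic model.

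By contrast, section 6.1.2 gives step-by-step non-convergence rules for the MMRM and for the categorical repeated measures model.

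**The concern.** Two treatments by two subgroup levels with an interaction make a saturated model: four parameters for four cell proportions. The interaction is a contrast of the four cell logits. A cell with no events has a logit of minus infinity, so the contrast has no finite value. Software then stops at an arbitrary large number with a huge standard error, and a Wald p-value from that fit means nothing. Fisher's test does not fill the gap, because it is assigned to the overall treatment comparison.

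At stake is a safety question that the plan raises itself: whether the effect of treatment on suicidality differs in adolescents with depression. If the model breaks down, the substitute would be chosen after the unblinded suicidality data are seen.

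**Working it through.** The SAP gives no event rate, no MDD prevalence and no figure for this analysis, so there is nothing of its own to reproduce.

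**Inputs.** From the SAP: about 184 patients randomized 1:1 (section 5.2), so 92 per arm, and the floor of 4 events in one arm (section 6.1.14.5). The CDI median split is taken as 46 and 46 per arm, ignoring ties. Assumed: 20% of patients with MDD, so 18 with and 74 without per arm; event rates of 3% to 10%, equal in all four cells.

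**1. What happens with an empty cell.** Illustrative data that meet the floor: duloxetine 2/18 with MDD and 2/74 without; placebo 0/18 and 3/74. Newton iterations for maximum likelihood give an interaction of 4.5, 9.5, 19.5 and 29.5 after 5, 10, 20 and 30 steps. The standard error goes from 3.4 to over 850,000. The fit diverges.

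**2. Chance of an empty cell, given the event counts.** Suppose k events in an arm fall at random over n1 and n0 patients. The chance that one of that arm's two cells is empty is

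e(k) = [C(n1,k) + C(n0,k)] / C(92,k) for k of 2 or more, and e(k) = 1 for k of 0 or 1.

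Over both arms it is 1 − [1 − e(k1)][1 − e(k2)].

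Median split:
- e(4) = 2 × 163,185 / 2,794,155 = 0.117
- e(2) = 2 × 1,035 / 4,186 = 0.494
- 4 and 4 events: 1 − 0.883² = 0.22
- 4 and 2 events: 1 − 0.883 × 0.506 = 0.55

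MDD, 18 and 74:
- e(4) = (3,060 + 1,150,626) / 2,794,155 = 0.413
- e(2) = (153 + 2,701) / 4,186 = 0.682
- 4 and 4 events: 1 − 0.587² = 0.66
- 4 and 2 events: 1 − 0.587 × 0.318 = 0.81

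| Events in the two arms | CDI median split | MDD 20% (assumed) |
|---|---|---|
| 4 and 4 | 22% | 66% |
| 4 and 2 | 55% | 81% |
| 4 and 0 or 1 | 100% | 100% |

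Only the 4 in one arm comes from the SAP. The second arm's count is varied to show the range.

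**3. Chance of an empty cell, given an event rate p.** The formula is 1 − {[1 − (1−p)^n1][1 − (1−p)^n0]}². At p = 5%:
- Median split: 0.95^46 = 0.0945, so 1 − 0.9055⁴ = 0.33
- MDD: 0.95^18 = 0.397 and 0.95^74 = 0.0225, so 1 − (0.603 × 0.978)² = 0.65

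| Assumed event rate | CDI median split | MDD 20% (assumed) |
|---|---|---|
| 3% | 68% | 86% |
| 5% | 33% | 65% |
| 8% | 8% | 40% |
| 10% | 3% | 28% |

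**4. Sensitivity at 5%.** An MDD share of 10% gives 87%, and 30% gives 46%. If the trial stopped with about 150 randomized (section 6.2), the two columns become 47% and 74%. If the higher-risk subgroup has three times the risk and the overall rate stays at 5%, they become 55% and 34%.

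**5. What a penalized fit returns.** For a saturated model, Firth's method equals adding 0.5 to the events and to the non-events of each cell. For the data in step 1:

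ln(2.5/16.5) − ln(2.5/72.5) − ln(0.5/18.5) + ln(3.5/71.5) = 2.07.

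With its standard error of 1.84, the 95% interval for the ratio of odds ratios is exp(2.07 ± 1.96 × 1.84), about 0.2 to 290. It is finite but says little. If placebo had no events at all, the 18/74 split alone would give a placebo subgroup odds ratio of (0.5/18.5)/(0.5/74.5) = 4.0.

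**The case against.** The strongest reply is that this is an implementation detail of a secondary safety analysis, and that the numbers follow the assumptions. Much of that stands.

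- A reader might infer from the two thresholds of 4 that the SAP expects few events. It does not say so. A floor for reporting is not a forecast. The broadest composite starts at a wish to be dead, and the trial admits patients with MDD, so a rate above 8% cannot be excluded.
- A reader might also infer that the model will often fail. That holds for rare outcomes and for an uneven MDD split. It does not hold for a composite at 10% with a median split, where the chance is 3%.
- The SAP names no estimator and no test. Maximum likelihood with a Wald test is the usual reading of an unqualified logistic regression. A likelihood-ratio test would still give a p-value with an empty cell, but the SAP does not name one, and the estimate would still be infinite.
- The events do not disappear. Section 6.1.14.5 lists every patient with ideation or behavior, at all visits.
- A penalized fit cannot create information. Step 5 shows that, with an empty cell, the penalty largely sets the answer, so it would be wrong to describe Firth's method as only slight shrinkage toward no effect.

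What remains is that the model is planned without condition, and that the floor "p-values will only be displayed if at least 4 events occurred in at least one treatment group" looks at one arm's total and not at the four cells.

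**Conclusion.** The point holds as a cheap improvement. Section 6.1.15 commits to a model whose interaction has no finite maximum likelihood estimate when any of the four cells is empty, and nothing in the SAP covers that case. At 4 events in one arm, the chance is 22% to 100% for the median split, depending on the other arm's count of 4 down to 0. That range assumes that events fall at random across the subgroup within each arm. The rate-based figures rest on assumed event rates and an assumed MDD share, and they fall quickly as events become more common. The documents do not support the stronger claim that breakdown is expected for every suicide-related outcome. Only a secondary safety subgroup analysis is affected. The primary BPI conclusion does not change.

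**What to change.** Amend section 6.1.15 for the C-SSRS outcomes as follows:

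- As the main presentation, show in each subgroup the event counts by arm and the risk difference with an exact confidence interval.
- Test the treatment-by-subgroup interaction by exact logistic regression, or by Firth's penalized likelihood, instead of ordinary maximum likelihood.
- State that when a cell is empty the Firth estimate is imprecise and largely set by the penalty, so the counts carry the interpretation.
- State whether the floor of 4 events in section 6.1.14.5 applies to this model.

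The cost is slightly more analysis work and intervals that are wide or one-sided. If an arm has no events, the exact conditional distribution of the interaction has a single point, so there is no test and the counts are the result.

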### **6.1.8. Patient Characteristics**

Patient allocation by investigator, grouped by country, will be summarized for Study Period II for all ITT patients.

Patient allocation by investigator will also be listed for all ITT patients.

The following patient characteristics will be summarized by treatment group for all ITT patients for Study Period II, and for those ITT patients entering the Study Period III.

- Demographic information: age, gender, ethnicity, race origin, country, height, weight, and BMI
- Baseline comorbid diagnoses: MDD, GAD, and ADD
- Baseline severity of illness measured by: BPI severity and interference ratings, PPQ pain ratings, CGI-Severity: Mental Illness, CGI-Severity: Overall Illness, FDI-child, and FDI-parent, CDI, and MASC
- Medical history: duration of fibromyalgia (years); onset of fibromyalgia (age); presence of fibromyalgia in family history (yes/no)
- Pre-existing conditions
- Historical alcohol and tobacco consumption
- Baseline concurrent/ongoing therapies for FM symptoms: 1) NSAIDS, 2) Physical therapy, and 3) Psychotherapy
- Historical illnesses
- Onset of menses (female patients only): incidence prior to or post study entry among female patients; age of onset of first menses, defined as (date of first menses)-(date of birth)

Baseline concurrent/ongoing therapies are those therapies which are started, ongoing or stopped at baseline (visit 1 to 2). Baseline concurrent/ongoing therapies include psychotherapy, physical therapy, and NSAIDs.

Comparisons between treatment groups will be performed using Fisher's exact test for categorical data and ANOVA with treatment and pooled investigative site as independent variables in the model for continuous data for Study Period II. Patient characteristics will be summarized for Study Period III without any statistical comparison between treatment groups.

A listing of patient demographic characteristics will be presented.

The pre-existing conditions table will present the number and percent of patients with pre-existing conditions by preferred term in decreasing frequency within MedDRA system organ class. Pre-existing conditions for ITT patients in Study Period II and all ITT patients entering

Study Period III are events reported at baseline (visit 1 to 2) regardless if they are resolved or ongoing at the time of randomization.

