Study Conduct – Concomitant Medications	Randomized patient reported prohibited concomitant medication use: <concomitant medication name>	For randomized patients, if any excluded medication (eg, SSRI, SNRI, stimulant, antipsychotic, benzodiazepine, anticonvulsant) is reported after Visit 2, then result is protocol deviation. Specify which concomitant medication in the protocol deviation details. Provide one record per patient per concomitant medication.
	Randomized patient who had consecutive use of NSAID less	For randomized patients in Study Period II, if patients had consecutive use of NSAID <

	
than 1 month immediately prior to visit 2 reported NSAID use: <NSAID name> exceeded 3 consecutive or exceeded 20 cumulative days during Study Period II
	
30 days (1 month) immediately prior to visit 2, and reported NSAID use exceeds 3 consecutive days or exceeds 20 cumulative days after visit 2 in SP II, then result is protocol deviation. Specify which NSAID in the protocol deviation details.

	
Randomized patient who had consecutive use of NSAID less than one month immediately prior to visit 8 reported NSAID use : <NSAID name> exceeded 3 days or exceeded 40 cumulative days during Study Period III
	
For randomized patients in Study Period III, if patients had consecutive use of NSAID < 30 days (1 month) immediately prior to visit 8, and reported NSAID use exceeds 3 consecutive days or exceeds 40 cumulative days after visit 8 in SP III, then result is protocol deviation. Specify which NSAID in the protocol deviation details.

	
Randomized patient reported opiate use : <opiate name> exceeded 3 consecutive or exceeded 20 cumulative days during Study Period II
	
For randomized patients in study Period II, opiate use exceeds 3 consecutive days or exceeds 20 cumulative days then result is protocol deviation. Specify which opiate in the protocol deviation details.

	
Randomized patient reported opiate use : <opiate name> exceeded 3 days/month or exceeded 40 cumulative days during Study Period III
	
For randomized patients in study Period III, opiate use exceeds 3 days/month or exceeds 40 cumulative days then result is protocol deviation. Specify which opiate in the protocol deviation details.

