### **6.1.12. Previous and Concomitant Therapy**

Previous therapies for fibromyalgia are those therapies for the treatment of fibromyalgia that started and stopped prior to or at baseline (Visit 2). Concomitant therapies include psychotherapy, physical therapy, and concomitant medication. Concomitant therapies for Study Period II are those which started prior to visit 2 or after visit 2 and are taken during SP II. Concomitant therapies for Study Period III are those that started prior to visit 8 or after visit 8 and are taken during SP III.

Previous therapies for fibromyalgia will be summarized by treatment group for all ITT patients, displaying the number and percentage of patients by preferred term for Study Period II and for all ITT patients entering Study Period III. Concomitant medications will be summarized in the same way for Study Period II and Study Period III, respectively. The tables will be sorted in decreasing frequency of preferred terms. The denominator used for calculating the percentages will be the total number of patients included in the ITT population for each treatment group for Study Period II, and will be the total number of patients included in the ITT patients entering Study Period III for each treatment group for Study Period III. Concomitant psychotherapy and

concomitant physical therapy will also be summarized by treatment group for Study Period II and Study Period III separately. Comparison between treatment groups will be performed using Fisher's exact test for Study Period II.

A listing of concomitant therapy will be presented for SP II and SP III.

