**Table HMGW.6.14 Definition of Subgroup Variables**

Subgroup Variable	Categories
1. Gender	1. Female or Male
2. Race Origin	2. White American Indian or Alaska Native Asian Black or African American Native Hawaiian or Other Pacific Islander Multiple
3. Baseline Pain Severity	3. ≤6 vs. >6 on BPI average pain severity at baseline
4. Family history of Fibromyalgia	4. Yes/No
5. Onset age of Fibromyalgia (years)	5. ≤12 vs. >12
6. Comorbid MDD	6. Yes/No
7. Comorbid GAD	7. Yes/No
8. Country	8. Country name
9. NSAID use (ongoing, concurrent regimen)	9. Yes/No

Abbreviations: BPI = Brief Pain Inventory; MDD = major depressive disorder; GAD = generalized anxiety disorder; vs. = versus, NSAID = non-steroidal anti-inflammatory drugs.

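### The NSAID-use subgroup is classified from medication taken during the study, so treatment can influence who falls in each category

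*SAP*

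**What the plan says.** Section 6.1.15 of the SAP announces that "For the BPI average pain severity, a subgroup analysis will be conducted for Study Period II". For each subgroup variable, "change from baseline to endpoint (LOCF and BOCF) in BPI average pain will be analyzed using an ANCOVA model", with terms added for subgroup and subgroup by treatment. The interaction, tested at 0.05, is called the primary test. In addition, "treatment group differences will be evaluated within each category of a subgroup regardless of the significance level of the treatment-by-subgroup interaction".

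One of the nine variables in Table HMGW.6.14 is "NSAID use (ongoing, concurrent regimen", coded yes or no. The only sentence that says how patients are classified is in the text of 6.1.15: "the NSAIDs use is based on concomitant medication took during study and medical review". It gives no visit window, no minimum duration and no criteria for the review.

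Three other places bear on this:

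- Section 6.1.12: "Concomitant therapies for Study Period II are those which started prior to visit 2 or after visit 2 and are taken during SP II".
- Section 6.1.8: "Baseline concurrent/ongoing therapies are those therapies which are started, ongoing or stopped at baseline (visit 1 to 2". NSAIDs are one of the three therapies covered.
- Table HMGW.6.2, for patients with less than 30 days of consecutive NSAID use before Visit 2: a deviation arises if "reported NSAID use exceeds 3 consecutive days or exceeds 20 cumulative days after visit 2 in SP II". Section 6.1.9 only lists such deviations.

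**The concern.** The other eight subgroup variables (gender, race origin, baseline pain, family history, onset age, MDD, GAD, country) are fixed at or before randomization. NSAID use, as written, is not. NSAIDs appear in Section 6.1.8 as therapy for fibromyalgia symptoms, and the outcome is average pain. It is plausible, though the SAP does not establish it, that patients whose pain does not improve take more of them. If so, duloxetine changes who becomes a user. Comparing arms within users or within non-users then compares patients who were not made alike by randomization.

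The within-category differences will be produced whatever the interaction test shows, so a biased contrast could be reported and read as effect modification by NSAID use. Separately, a medical review without criteria lets two analysts classify the same patient differently, even if there is no bias at all.

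**Working it through.** **Text.** The classification sentence points to use during the study. Section 6.1.12 includes therapy started after Visit 2. Table HMGW.6.2 shows that such use is foreseen and is flagged only above a threshold. The table label suggests an established regimen but sets no window, and 6.1.15 does not refer to the Visit 1 to 2 definition in 6.1.8. Read literally, use during the study could also include Study Period III, although the analysis is for Study Period II.

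**Size.** The SAP gives no figure for this subgroup, so there is nothing of its own to reproduce. From Section 5.2 I take 184 patients, 1:1, and a difference of 1.0 point. The SD of change, the share of baseline users, the rate of starting NSAIDs and the strength of the pain-use link are not given; all are assumptions.

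Outcome model, with the same true effect in everyone:

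change = -2 - 1.0 × trt + u + e, with u and e each of SD 1.5, so total SD = √(1.5² + 1.5²) = 2.12.

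- Model A, all use depends on pain: logit P(use) = -0.3 + s × (-1.0 × trt + u).
- Model B, user = baseline user (probability 0.30, independent of arm) or starter, with logit P(start) = -1.0 + s × (-1.0 × trt + u).

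The odds ratio for use per SD of u is exp(1.5s): 1.0, 1.6, 2.5 and 6.0 at s = 0, 0.3, 0.6 and 1.2. Effects below come from 2,000,000 simulated patients per setting. Rejection rates for Model B come from 20,000 trials of 184, with treatment, subgroup, their product and a baseline covariate in the model.

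| s | A: non-users / users | B: non-users / users | B: interaction (users minus non-users) | B: interaction test rejects |
|---|---|---|---|---|
| 0 | -1.00 / -1.00 | -1.01 / -1.00 | about 0 | 4.9% |
| 0.3 | -0.96 / -0.95 | -0.97 / -1.01 | -0.05 | 5.2% |
| 0.6 | -0.87 / -0.85 | -0.90 / -1.03 | -0.13 | 5.6% |
| 1.2 | -0.71 / -0.64 | -0.75 / -1.05 | -0.30 | 8.0% |

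Interactions were taken before rounding the two effects; in Model A the shift is at most 0.06. In Model A both categories are attenuated, because a duloxetine patient needs a worse underlying u than a placebo patient to become a user. In Model B baseline users dilute this in the user category but not among non-users, and the gap appears as an interaction.

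With the subgroup fixed at baseline, Model B gives -0.99 to -1.01 in both categories and rejection of 4.9% to 5.4%.

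**Simulation error.** For a 5% rate in 20,000 trials the standard error is √(0.05 × 0.95 / 20,000) = 0.15 percentage points. So 5.2% is not distinguishable from 5%, 5.6% is a small excess, and 8.0% is clear. Repeat runs at s = 1.2 gave 7.7% and 7.8%.

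**Precision.** Mean stratum standard errors at 184 patients are 0.36 to 0.50. The largest biases are 1.00 - 0.64 = 0.36 for users (standard error 0.48 to 0.50 in Model A) and 1.00 - 0.71 = 0.29 for non-users (0.36 to 0.41).

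**Different assumptions.** A second set used SD 2.18, the value implied by 80% power with 0.81 × 92 = 74.5 per arm: 1/[(1.960 + 0.842) × √(2/74.5)] = 2.18. Starting an NSAID depended on the pain change itself, with probability 30% at the placebo mean. At a log-odds slope of 1.0 per point:

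| Baseline users | Non-users / users | Interaction |
|---|---|---|
| 0% | -0.68 / -0.57 | +0.11 |
| 20% | -0.68 / -0.95 | -0.28 |
| 40% | -0.68 / -1.03 | -0.34 |

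At slope 0 there is no bias. The direction of the spurious interaction therefore depends on the use pattern.

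**The case against.** The strongest counter-argument concerns importance. The variable is one of nine in a secondary analysis without multiplicity adjustment, the bias is below one stratum standard error in Models A and B, and the clear excess in rejection needs an odds ratio of about 6 per SD of u. Nine interaction tests on two endpoints already carry more false-positive risk than this adds. The simulation omits pooled site and dropout and does not model the LOCF or BOCF endpoints. All of that stands, and it limits the weight of the point.

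On the text, the table label resembles the baseline wording of Section 6.1.8, and a reading confined to Study Period II is the natural one because the analysis is declared for that period. Both are fair. Neither removes the defect: use within Study Period II is still after randomization, and the classification sentence neither cites 6.1.8 nor sets a baseline limit.

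The protocol, not shown here, may say which NSAID regimens are permitted, and the SAP does not say that the medical review is unblinded. The missing review criteria are therefore a lesser, reproducibility matter.

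**Conclusion.** The concern holds. Followed as written, Section 6.1.15 conditions the within-category contrasts and their interaction test on a variable that treatment can change, and the text and table label do not settle on one definition. Whether bias occurs depends on a link between pain response and NSAID use, which the SAP neither states nor excludes.

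Under the assumed models a uniform effect of -1.0 shows as -0.97 to -0.85 in the affected categories at weak to moderate links, and as -0.75 to -0.57 at the strongest links tried. The spurious interaction ranges from +0.11 to -0.34. This is a modest problem confined to one subgroup variable, and the primary MMRM contrast does not use it. It should be corrected because the remedy is already in the SAP and removes the bias.

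**What to change.** Define the NSAID subgroup as baseline concurrent or ongoing NSAID therapy at Visits 1 to 2, by reference to Section 6.1.8, and reword both the sentence in 6.1.15 and the label in Table HMGW.6.14 to that one definition. If a medical review is kept, state its criteria and restrict it to blinded data from before randomization. Report NSAID use during the study only by arm, as Section 6.1.12 already provides for concomitant medications.

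The cost is one sentence and one table label. No new data are needed, because the baseline variable is already defined and summarized. The change should be made before unblinding, so that the choice of definition cannot depend on the results.
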